 - d. Known bleeding disorder (e.g., dysfibrinogenemia, factor IX deficiency, haemophilia, Von Willebrand's disease, Disseminated Intravascular Coagulation [DIC], fibrinogen deficiency, or other clotting factor deficiency)
 - e. Receiving therapeutic anticoagulation
15. Evidence at the time of Screening of significant renal or hepatic insufficiency (unless due to haemolysis, or leukaemic infiltration) as defined by any one of the following local lab parameters:
 - a. Calculated glomerular filtration rate (GFR) < 40 mL/min or serum creatinine > 1.5 x the local upper limit of normal
 - b. Aspartate transaminase (AST) or alanine aminotransferase (ALT) ≥ 2 x the local upper limit of normal
16. Use of an investigational agent within less than 14 days, or the equivalent of at least 7 half-lives of that agent, whichever is the longer, prior to the start of study treatment.
17. Pregnant or lactating females.

CCI

CCI

IMG-7289 Dose Limiting Toxicity (DLT): Dose Escalation, Combination Therapy and Duration Extension Decision Making Rules; and, Maximum Tolerated Dose (MTD), Maximum Tolerated Duration (MTD_u):

Adverse event intensity will be evaluated using the National Cancer Institute (NCI) Common Terminology Criteria for Adverse Events (CTCAE) version 4.03, published 14 June 2010.

Definitions:

Haematologic Toxicity: Haematologic values outside of the normal reference range are inherent features of AML and MDS, and are expected effects of many therapeutic attempts to manage these diseases. The effects of IMG-7289 on normal myeloid haematopoiesis observed in non-clinical studies are expected in humans; these are pharmacodynamic effects of LSD1 inhibition by IMG-7289, thus are not regarded as adverse. These events, with the

exceptions noted below, will not be considered DLTs. Additional information pertaining to haematologic toxicity, DLTs, dose escalation/duration extension rules, and MTDs is provided in Section 8.2.

Dose limiting toxicity (DLT): Any one of the following AEs that occurs during the first cycle and is considered by the Investigator possibly, probably or definitely related to IMG-7289:

- A clinically significant bleeding event;
- Any Grade 4 or 5 non-haematologic adverse event;
- Any Grade 3 non-haematologic adverse event with failure to recover to Grade 1 within 7 days of drug cessation, with the following exceptions:
 - ≥ Grade 3 nausea, vomiting or diarrhoea that responds to standard medical care

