If the DSMC determines combination therapy should proceed, then additional sub-cohorts will commence.

Sub-cohort 1w: Dosing will begin on Day 1 with IMG-7289 (dose to be determined by the DSMC) dosed for 7 days on followed by 7 days off, in combination with ATRA 45 mg/m² per day dosed for 21 days[§] on followed by 7 days off.

[§]Patient's enrolled in Sub-cohort 1χ will continue their current treatment regimen until completion of their initially allowed treatment cycles and pending DSMC review of the sentinel patient in Sub-cohort 1w, after which transition to the new (21 day ATRA) regimen may occur at the start of the next cycle.

If the DSMC determines that combination therapy offers greater therapeutic benefit as compared to single agent IMG-7289 therapy, then patients who have fully completed their initially allowed IMG-7289 treatment cycles and are receiving a different treatment regimen (i.e., IMG-7289 alone) will be transitioned to combination therapy at the start of their next cycle.

The table below summarizes the IMG-7289 in combination component of the dose-finding phase by sub-cohort, dose, dosing duration, rest period, and number of initially allowed IMG-7289 cycles.

Table 2: Combination Therapy Component of the Dose-finding Cohort

Sub-cohort	IMG-7289 Dose (free base)	IMG-7289 Cycle		No. of Initial IMG-7289 Cycles**
		Dosing Duration	Rest Period*	
1 χ	TBD [¥]	7 days on	7 days off	4
	Administered in combination with			
	ATRA [§] 45 mg/m ² /d for 7 days [§] on followed by 7 days off			
1w [§]	TBD [¥]	7 days on	7 days off	4
	Administered in combination with			
	ATRA [§] 45 mg/m ² /d for 21 days on followed by 7 days off			

*The duration of the rest period may be adjusted based on an assessment by the DSMC that either a specific patient or an entire cohort could benefit from an extended rest period. This decision could be taken if there is no clear indication of the restoration of normal haematopoiesis in the 7 day period or analysis of the pharmacokinetic parameters in the earlier sub-cohorts suggest the rest period duration requires adjusting; for example, if the half-life of IMG-7289 is unexpectedly long. Investigators will be notified of any such change.

**Additional cycles may be allowed, contingent on clinical benefit/patient response.

[¥]The IMG-7289 dose for administration with ATRA will be determined by the DSMC based on ongoing review of safety and pharmacodynamic data.

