8 DATA SAFETY MONITORING COMMITTEE (DSMC) REVIEWS AND MANAGEMENT OF STUDY TOXICITIES

8.1 Data Safety Monitoring Committee (DSMC) Reviews

Safety will be monitored throughout the study in accordance with a Data Safety Monitoring Plan (DSMP) by a DSMC constituted by, at a minimum: the Imago BioSciences Principal Medical Monitor, a Principal Investigator and an Independent designee, an AML clinical trials specialist with extensive clinical experience. To ensure a quorum of 3 members at all meetings, an alternate DSMC member will also routinely attend Safety Reviews, and participate when needed.

During all phases, the DSMC will review safety parameters, pharmacodynamic (PD) markers and pharmacokinetic (PK) parameters to form conclusions around the safety and pharmacodynamic effect of differing doses, treatment regimens and dosing durations. DSMC reviews are critical, as neither a new dose-finding sub-cohort, nor a duration-finding cohort may commence without DSMC review and recommendation to do so. The DSMC will assess: the safety of each dose and dosing duration, with and without ATRA. The DSMC will also assess: any clinically significant biochemistry trends; the impact of each dose on normal myeloid haematopoiesis; the PD impact of each dose on malignant cells, and whether further cohorts/sub-cohorts in each respective phase are appropriate.

Data from each cohort/sub-cohort will be reviewed by the DSMC after a minimum of 3 patients in a cohort/sub-cohort have completed Cycle 1 and prior to dosing the next cohort/sub-cohort. Safety data to be evaluated, may include: clinical laboratory results, ECGs [ECGs required in the first 9 patients only as there have been no non-clinical cardiovascular findings; if clinically meaningful trends in ECGs are noted, then the DSMC will make a recommendation as to the appropriate action to be taken (i.e., cardiologist consult, additional ECG requirements, etc.); physical examination and vital sign measurements; and AEs/DLTs/Medical Events of Interest (MEOIs). A combination of PD and PK markers will be evaluated, as available, and may include: peripheral white blood cell count; peripheral blast count; reticulocyte count; platelet count; bone marrow blast count; expected changes in immunophenotype; changes in VAF, changes in cytokine profiles; and, changes in PSA (males only). These metrics will be evaluated in the context of PK parameters such as changes in

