DSMC reviews during the IMG-7289 in combination with ATRA component of the dose-finding phase are detailed below.

Combination therapy (see Section 7.2.2.1) will proceed in sub-cohorts (i.e., Sub-cohort 1w, 1v, etc.) provided that:

1. A minimum of 3 patients from the previous sub-cohort have completed Cycle 1, both the applicable dosing and rest periods
2. The number of patients who experience DLT is within the guidelines (Section 8.2.2)
3. DSMC review of the previous sub-cohort has determined that:
 - a. The doses administered in combination appear safe
 - b. Further combination therapy is appropriate

Upon DSMC confirmation that no further dose-finding sub-cohorts are anticipated, the DSMC will also make a determination of whether it is safe to extend the dosing duration, to determine whether longer durations are associated with greater therapeutic benefit. The study will then progress to assess the effect of IMG-7289 dosing duration.

DSMC reviews during the duration-finding phase are detailed below.

During the duration-finding phase, the DSMC will assess whether the longer duration of IMG-7289 dosing, with and without ATRA, at the D_p is safe and associated with greater therapeutic benefit using a combination of PD and PK markers. Each duration cohort will be separated by approximately one week to allow for completion and analysis of appropriate safety assessments required for provision to the DSMC.

There are two potential duration-extension pathways for the duration-finding cohorts: duration extension with IMG-7289 alone, or IMG-7289 administered in combination with ATRA. Therefore, prior to opening a duration-finding cohort, the DSMC will assess the safety and pharmacodynamic effects of the earlier sub-cohorts, and reach consensus on:

1. Whether it appears safe to extend the duration of IMG-7289 dosing
2. Whether there appears to be greater therapeutic benefit with IMG-7289 dosed in combination with ATRA.

Based on the above assessments, one of the duration-finding cohorts will commence.

The duration of dosing (see Section 7.2.2.3) will be extended in subsequent cohorts provided that:

1. A minimum of 3 patients in the previous cohort have completed Cycle 1, both the applicable dosing and rest periods
2. The number of patients who experience DLT is within the guidelines (see Section 8.2.2)
3. DSMC review of the previous cohort has determined that:
 - a. The duration of dosing appears safe
 - b. Further duration extension is appropriate

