The intended dosing plan for high risk AML/MDS patients is predicated on the supposition that LSD1 must be maximally inhibited to achieve the greatest therapeutic benefit. The concentrations of LSD1 inhibitors such as IMG-7289 (free base) used to achieve maximal effects on growth, differentiation and apoptosis *in vitro* with primary patient-derived AML cells as well as AML cell lines are similar to concentrations that *in vivo* inhibit red cell, platelet and granulocyte production. It is therefore expected that high risk AML/MDS patients will require treatment at doses sufficient to induce profound thrombocytopenia and neutropenia. These drug-induced but reversible cytopenias can be managed clinically as needed with platelet and red cell transfusions as well as broad-spectrum antibiotics in the case of febrile neutropenia, as are already standard practices in the routine management of AML/MDS patients receiving intensive SOC chemotherapy.

The effects of IMG-7289 on normal myeloid haematopoiesis observed in non-clinical studies are expected in humans; these are pharmacodynamic effects of LSD1 inhibition by IMG-7289, thus are not regarded as adverse. These events, with the exceptions noted below, will not be considered DLTs.

Dose Limiting Toxicity (DLT): DLT is defined as any one of the following AEs that occurs during the first cycle of therapy and is considered by the Investigator to be possibly, probably or definitely related to IMG-7289.

- A clinically significant bleeding event;
- Any Grade 4 or 5 non-haematologic adverse event;

- Any Grade 3 non-haematologic adverse event with failure to recover to Grade 1 within 7 days of drug cessation, with the following exceptions:
 - ≥ Grade 3 nausea, vomiting or diarrhoea that responds to standard medical care
 - ≥ Grade 3 aesthenia lasting less than 14 days
- Any Grade 3 electrolyte abnormality unrelated to the underlying malignancy and persisting greater than 24 hours.

Patients who experience a dose limiting toxicity (DLT) will have their dose adjusted downward if the Medical Monitor and Principal Investigator deem it safe for the patient to continue on IMG-7289. To ensure a minimum of 3 Cycle 1 completers, and contingent on the number of prior DLTs within the sub-cohort/cohort, such patients may be replaced.

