Any patient that experiences a DLT that results in discontinuation of IMG-7289 therapy may begin alternative therapy after a one week washout period and if their physician deems this safe and appropriate regarding the resolution of the DLT.

Please consult the Medical Monitor for IMG-7289 dose modifications for the management of clinically significant changes in platelets, neutrophil counts, or other haematologic parameters.

Expected toxicities based on non-clinical studies with IMG-7289 are reported in the latest edition of the Investigator's Brochure.

CCI

CCI

Additionally, the DSMC may review safety data and, even in the absence of 2 DLTs, deem that the safe dose has been exceeded. Were this to occur, dose escalation would cease.

Table 5: IMG-7289 Dose Limiting Toxicity and Escalation Decision*

Patients with DLT at a Given Dose	Escalation Decision Rules
0-1 out of 3	Open subsequent sub-cohort/next dose
2 out of 3	Dose escalation will be stopped

*The above instruction applies in kind for combination therapy and duration extension decision making.

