8.2.3 IMG-7289 Maximum Tolerated Dose (MTD) and Duration (MTD_u)^φ

The MTD is defined as the highest dose below or at which <2 out of 3 patients experience DLT. If unacceptable toxicity occurs (DLT in 2 out of 3 patients) at the reduced dose of 0.375 mg/kg/d, then the dose will be further reduced to the 0.1875 mg/kg/d dose. In this study, the MTD may not be reached if the highest dose tested is found to be safe (that is, DLT in <2 out of 3 patients).

The above instruction applies in kind for the MTD_u.

^φMTD and MTD_u definitions also apply to combination therapy sub-cohorts.

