8.3 ATRA Toxicity

[figure not shown]
Decisions on IMG-7289 and ATRA dose interruption, reduction and re-challenge due to observed toxicity will be made by the Investigator in consultation with Medical Monitor and DSMC.

Expected toxicities for ATRA can be found in the Product Information (PI) document.

CCI

CCI

[figure not shown]

[figure not shown]
CCI

CCI

CCI

CCI

CC

[figure not shown]

CCI

CCI

[figure not shown]

[figure not shown]

CCI

CCI

[figure not shown]

CC

CCI

CCI

CCI

CCI

CCI

CCI

CCI

CCI

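### In the IMG-7289 plus ATRA cohorts, the visible 2-of-3 rule and the combination MTD/MTDu count only Cycle 1 events at least possibly related to IMG-7289, so ATRA-only toxicity is left to judgement (a minor gap, most relevant within 1w)

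*Protocol*

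**What the plan says.** The protocol defines a DLT twice, and both versions tie it to one drug. Section 8.2.1 requires that the event "occurs during the first cycle of therapy and is considered by the Investigator to be possibly, probably or definitely related to IMG-7289". The synopsis also requires that it be "considered by the Investigator possibly, probably or definitely related to IMG-7289". No visible DLT criterion names ATRA.

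That count is then carried into the combination cohorts in three places:

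- **Section 8.1**, condition 2 for opening a further combination sub-cohort: "The number of patients who experience DLT is within the guidelines (Section 8.2.2").
- **Table 5**, where 0-1 of 3 proceeds and 2 of 3 stops. Its footnote says: "The above instruction applies in kind for combination therapy and duration extension decision making". This is how 3χ and 4χ come under the rule.
- **Section 8.2.3**, whose footnote says that the MTD and MTDu "definitions also apply to combination therapy sub-cohorts".

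ATRA toxicity has its own Section 8.3. Its text covers changes to either drug: "ATRA dose interruption, reduction and re-challenge due to observed toxicity will be made by the Investigator in consultation with Medical Monitor and DSMC". The visible text gives no count or threshold. Condition 3a in Section 8.1 separately requires the DSMC to judge the combined doses safe, and the text above Table 5 lets the DSMC stop without 2 DLTs.

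**The concern.** The rule was written for a single agent and extended to a two-drug regimen without widening the attribution. Suppose 2 of 3 combination patients had DLT-grade events in Cycle 1 that the Investigator put down to ATRA alone. The count would be 0 of 3. Condition 2 would be met, and so would the definition of the combination MTD. The DSMC could still stop the regimen, but stopping it would not change what the MTD definition says.

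Safety and tolerability with and without ATRA is a primary endpoint (Section 12.4.1). A combination MTD that reflects only the IMG-7289-attributed part of the toxicity does not fully describe the regimen. It also depends on how causality is divided between two drugs given together, open-label.

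**Working it through.** **1. Where attribution can separate the drugs.** Inputs are Sections 5.1, 7.2.2.1 and 7.2.2.3 (Tables 2 and 4) and 16.1.3 footnote o.

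| Cohort | IMG-7289 days in Cycle 1 | ATRA days in Cycle 1 | ATRA days without IMG-7289 dosing in Cycle 1 |
|---|---|---|---|
| 1χ | 7 of 14 | 7 of 14 | 0 |
| 1w | 7 of 14 | 14 of 14 | 7 (Days 8-14) |
| 3χ | 14 of 21 | 14 of 21 | 0 |
| 4χ | 21 of 28 | 21 of 28 | 0 |

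Only 1w has ATRA dosing without IMG-7289 dosing inside the DLT window. Of its 21 ATRA days, 14 (14/21 = 67%) fall in Cycle 1. Days 15-21 fall in Cycle 2, after the window closes for either drug.

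**2. How much IMG-7289 is still on board.** Section 3.7 gives a half-life of 4-5 days. Assuming first-order elimination, the fraction of the Day 7 level left on Day 14 is 2^(-7/4) = 0.30 to 2^(-7/5) = 0.38. Section 3.7 itself says exposure in the rest week stays at or above the IC50.

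**3. Effect on the numeric rule.** The documents give no target DLT rate or operating characteristics, so there is no figure of theirs to reproduce. All rates below are assumed. Let p be the true Cycle 1 rate of DLT-grade events from either drug and s the share called ATRA-only. The counted rate is c = p(1 - s), and

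P(0-1 of 3 counted) = (1 - c)^3 + 3c(1 - c)^2.

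Example: p = 0.40 and s = 0.10 give c = 0.36, and 0.64^3 + 3 × 0.36 × 0.64^2 = 0.262 + 0.442 = 0.705.

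| p | s = 0 | s = 5% | s = 10% | s = 25% |
|---|---|---|---|---|
| 0.10 | 97.2% | 97.5% | 97.7% | 98.4% |
| 0.20 | 89.6% | 90.5% | 91.4% | 93.9% |
| 0.33 | 74.5% | 76.7% | 78.8% | 84.7% |
| 0.40 | 64.8% | 67.7% | 70.5% | 78.4% |
| 0.50 | 50.0% | 53.7% | 57.5% | 68.4% |

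Against s = 0, the gain in passing is 0.3 to 3.7 points at 5%, 0.5 to 7.5 at 10% and 1.2 to 18.4 at 25%. The s = 0 column shows that most of the pass probability comes from the 2-of-3 rule itself.

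**4. The same question as extra toxicity.** Let a be the IMG-7289-attributed rate and b the rate of ATRA-only events, assumed independent. If both count, the rate is 1 - (1 - a)(1 - b). P(stop) now, then with ATRA-only events counted:

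| a | Now | b = 0.02 | b = 0.05 | b = 0.10 | b = 0.20 |
|---|---|---|---|---|---|
| 0.10 | 2.8% | 3.8% | 5.7% | 9.5% | 19.1% |
| 0.20 | 10.4% | 12.0% | 14.5% | 19.1% | 29.5% |
| 0.30 | 21.6% | 23.4% | 26.1% | 30.9% | 41.0% |

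The difference is 1 to 4.5 points for b up to 0.05, about 7 to 9 at 0.10, and 16 to 19 at 0.20. The gap is small only if ATRA-only events of DLT grade are uncommon. Neither table includes the DSMC gate.

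**The case against.** The strongest defence is that the scope is deliberate. Section 8.2.1 and Table 5 are titled for IMG-7289, ATRA is an approved drug with its own section, and IMG-7289 is the drug being dose-found. Toxicity unrelated to it should not set its MTD. That stands for the single-agent MTD. It does not explain why the same count also defines a combination MTD.

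Three further points stand and limit the size:

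- Section 11.2.2 rates an event Possible unless a relationship can be definitively excluded, and SAP Section VI.C treats missing relatedness as possible. Few events should escape the count.
- Section 3.7 regards 21-day ATRA as safe because it is less exposure than the 45-60 days usual in APL.
- The DSMC reviews all AEs, must be satisfied on the combined doses, and can reduce ATRA dose or duration.

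A reader might infer more than the documents support:

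- **That toxic combinations advance unchecked.** They cannot: condition 2 opens nothing without condition 3a.
- **That the added ATRA days go unseen because the sentinel is dosed for 7 days, or that 1χ patients move on that basis** ("transition to the new (21 day ATRA) regimen may occur at the start of the next cycle"). The sentinel gate is not the DLT count. Full review needs 3 patients through dosing and rest, so Days 8-14 are seen. The move by 1χ patients awaits DSMC review and completion of their initial cycles.
- **That the flawed count opens 1w.** The count that opens 1w comes from 1χ, where both drugs run the same days.
- **That causality is not recorded per drug.** Section 11.2 mentions one relationship to study drug, but the CRF is not in the documents and SAP text after AE severity is redacted.
- **That no ATRA threshold exists anywhere.** Parts of 8.2.2 and the text after 8.3 are redacted, and the Data Safety Monitoring Plan is not available.

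**Conclusion.** The point holds as a minor design gap. As visibly written, the 2-of-3 rule and the combination MTD/MTDu measure IMG-7289-attributed toxicity, not regimen toxicity. The single-agent IMG-7289 MTD is not made wrong, and all AEs are still recorded and reviewed.

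The practical effect is probably a few percentage points in the numeric rule. That rests on assumed rates, on ATRA-only attribution being uncommon, and on ignoring the DSMC, which would reduce the effect further. The count within 1w is where it matters most. In 1χ, 3χ and 4χ the two drugs are dosed on the same days, so the attribution rule is the same but there is less room to separate them. Confidence is medium because of the redacted and unavailable text.

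**What to change.** For combination cohorts only, reword the DLT definition in Section 8.2.1 and the synopsis so that an event counts if it is at least possibly related to IMG-7289, to ATRA or to the two together. Use that count for Table 5 and for the combination MTD/MTDu. Leave the list of DLT events unchanged.

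Add a statement to Section 8.2.2: if 2 of 3 is reached only through ATRA-attributed events, that combination regimen exceeds the combination MTD/MTDu and ATRA is adjusted under Sections 8.1 and 8.3, while the single-agent IMG-7289 MTD/MTDu is unaffected. Report the IMG-7289-only count alongside, and record causality per drug if the CRF does not already do so. If the Data Safety Monitoring Plan already holds such a threshold, cite it in Section 8.2.2 and check that the combination MTD/MTDu uses it.

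The cost is one phrase in two places, a short addition to Section 8.2.2 and possibly one CRF field. Combination progression may slow slightly, because some purely ATRA toxicity would count. The change does not bring ATRA Days 15-21 of 1w into the count; those depend on the length of the DLT window, which is a separate choice.

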8.2.3 IMG-7289 Maximum Tolerated Dose (MTD) and Duration (MTD_u)^φ

The MTD is defined as the highest dose below or at which <2 out of 3 patients experience DLT. If unacceptable toxicity occurs (DLT in 2 out of 3 patients) at the reduced dose of 0.375 mg/kg/d, then the dose will be further reduced to the 0.1875 mg/kg/d dose. In this study, the MTD may not be reached if the highest dose tested is found to be safe (that is, DLT in <2 out of 3 patients).

The above instruction applies in kind for the MTD_u.

^φMTD and MTD_u definitions also apply to combination therapy sub-cohorts.

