 - ≥ Grade 3 asthenia lasting less than 14 days
- Any Grade 3 electrolyte abnormality unrelated to the underlying malignancy and persisting greater than 24 hours.

Patients who experience a DLT may have their dose adjusted downward if the Medical Monitor and Principal Investigator deem it safe for the patient to continue on IMG-7289. To ensure a minimum of 3 Cycle 1 completers, and contingent on the number of prior DLTs within the cohort, such patients may be replaced.

Please consult the Medical Monitor for IMG-7289 dose modifications for the management of clinically significant changes in platelets, neutrophil counts, or other haematologic parameters.

Expected toxicities based on non-clinical studies with IMG-7289 are reported in the latest edition of the Investigator's Brochure.

IMG-7289 Dose Escalation, Combination Therapy and Duration Extension Decision Rules:

The DSMC will convene and review safety data after a minimum of 3 patients in a sub-cohort/cohort have completed Cycle 1 (both the treatment and rest periods). If 0-1 of 3 patients experience a DLT, and if the DSMC deems safe, then dose escalation will proceed to the next higher dose with the opening of the applicable sub-cohort/cohort. If 2 out of 3 patients experience a DLT, then the safe dose has been exceeded, enrollment in the sub-cohort/cohort will close and dose escalation cease.

The table below outlines these rules.

Patients with DLT at a Given Dose	Escalation Decision Rules*
0-1 out of 3	Open subsequent sub-cohort/next dose
2 out of 3	Dose escalation will be stopped

*The above instruction applies in kind for combination therapy and duration extension decision making.

As this study is not investigating the effects of cytotoxic agents, the 2 DLT/3 patient rule should provide an adequate safety margin to patients, while allowing escalation to doses that could offer greater therapeutic benefit. This study design does not conform to the traditional 3+3 dose escalation study which is based on pre-specified rules using actual observations of target events such as dose-limiting toxicity. The traditional 3+3 design was developed in an era of cytotoxic drugs and is appropriate when the toxicity is directly proportional to exposure. This study takes the alternative model-based approach more appropriate for a targeted, non-cytotoxic drug such as IMG-7289, in which there is no observed monotonic relationship between exposure and toxicity (Le Tourneau, *et al.*, 2009). Specifically, this

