study employs the dose-toxicity model developed in rat and dog relating the plasma concentration of drug 24 hours after last dose at steady state needed to inhibit platelet production, a process dependent on the activity of LSD1.

Additionally, the DSMC may review safety data and, even in the absence of 2 DLTs, deem that the safe dose has been exceeded. Were this to occur, dose escalation would cease.

IMG-7289 Maximum Tolerated Dose (MTD) and Maximum Tolerated Duration (MTD_u)^φ:

MTD: The highest dose below or at which <2 out of 3 patients experiences DLT.

MTD_u: The longest duration below or at which <2 out of 3 patients experiences DLT.

^φMTD and MTD_u definitions also apply to combination therapy sub-cohorts.

The MTD may not be reached in this study if the highest dose tested is found to be safe.

ATRA Toxicity: Decisions on IMG-7289 and ATRA dose interruption, reduction and re-challenge due to observed toxicity will be made by the Investigator in consultation with Medical Monitor and DSMC.

Expected toxicities for ATRA can be found in the PI.

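### The MTD definition counts DLTs only and does not say what becomes of a dose that the DSMC rules too high without two DLTs

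*Protocol*

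**What the plan says.** **Definition.** Protocol Section 8.2.3: "The MTD is defined as the highest dose below or at which <2 out of 3 patients experience DLT". The synopsis has the same rule: "MTD: The highest dose below or at which <2 out of 3 patients experiences DLT". Section 8.2.3 carries it over in kind to the maximum tolerated duration (MTDu), and a note extends both definitions to the combination sub-cohorts.

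**'Not reached' clause.** Section 8.2.3 adds that the MTD may not be reached if "the highest dose tested is found to be safe (that is, DLT in <2 out of 3 patients", where the bracket closes. The synopsis has a similar sentence without the bracketed explanation.

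**Two routes to 'exceeded'.** The synopsis gives the count route: "If 2 out of 3 patients experience a DLT, then the safe dose has been exceeded". The text just before Table 5, and the synopsis, give the committee route: the DSMC may, "even in the absence of 2 DLTs, deem that the safe dose has been exceeded". The only consequence stated for a committee ruling is that escalation ceases.

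**Duration.** The committee route speaks of dose. The note to Table 5 reads: "The above instruction applies in kind for combination therapy and duration extension decision making". Section 8.1 makes extension of duration depend on the DLT count and, as a separate condition, on a DSMC finding: "The duration of dosing appears safe".

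**What a DLT is.** Section 8.2.1 limits DLTs to "any one of the following AEs that occurs during the first cycle of therapy" and judged at least possibly related to IMG-7289. Expected effects on normal myeloid blood formation are kept out, apart from listed exceptions such as clinically significant bleeding.

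**The concern.** The protocol uses one phrase for the result of both routes, yet only one route enters the MTD. A dose that the trial's own safety committee has ruled too high can still satisfy the definition.

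The case is not far-fetched, because the two routes look at different things. Section 8.2.1 expects effective doses to cause profound thrombocytopenia and neutropenia, excludes these from the DLT count (bleeding aside), and stops counting after Cycle 1. In the visible text, a DSMC ruling is the only way that such cytopenias, or toxicity in later cycles, can mark a dose as too high.

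At stake is a label in the study report: 'maximum tolerated', or 'limit not reached', attached to a dose that the committee rejected.

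**Working it through.** The plan gives no figure for the MTD rule, so there is none to reproduce. The check applies the rule to every possible outcome at the top dose.

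**Inputs.** Doses 0.75, 1.5, 3 and 6 mg/kg/d come from Table 1, where 6 is one of the two options for Sub-cohort 1d. Assumed for illustration: 0 of 3 DLTs and no DSMC objection at the three lower doses.

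**Rule as written.** MTD = highest dose with fewer than 2 of 3 DLTs.

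**Corrected rule.** MTD = highest dose with fewer than 2 of 3 DLTs that also lies below any dose with 2 or more DLTs or with a DSMC ruling that the safe dose was exceeded.

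| DLTs of 3 at 6 mg/kg/d | DSMC rules 6 too high? | Dose returned as written | Dose returned, corrected |
|---|---|---|---|
| 0 | no | 6 | 6 |
| 0 | yes | **6** | **3** |
| 1 | no | 6 | 6 |
| 1 | yes | **6** | **3** |
| 2 | no | 3 | 3 |
| 2 | yes | 3 | 3 |
| 3 | no | 3 | 3 |
| 3 | yes | 3 | 3 |

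The two rules differ only in the rows with 0 or 1 DLT and an adverse ruling. In the two rows with 0 or 1 DLT and no ruling, no dose was exceeded. The proper label there is 'MTD not reached, highest dose tested 6', which the current text already allows.

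**The 'not reached' clause in the disputed rows.** Section 8.2.3 equates 'safe' with fewer than 2 of 3 DLTs. With 0 or 1 DLT the rejected dose passes that test, so 'safe, MTD not reached' is also open. Both available labels ignore the ruling.

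**Search for a correction elsewhere.**
- Protocol 7.2.2.2 lets the DSMC find the starting dose too high, but the further step-down from 0.375 mg/kg/d again uses 2 of 3.
- Protocol 8.1 has the DSMC convene when an MTD or MTDu appears to be reached, and refers to 8.2.3 for what that means.
- SAP Section IV.A refers back to Protocol Section 8 and to 8.2.3. The visible SAP gives no definition of its own.

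None of these carries a DSMC ruling into the MTD.

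**The case against.** **A coherent reading exists.** Both routes share one phrase and both stop escalation. Cohort progression needs both an acceptable DLT count and a DSMC view that the dose or duration appears safe. The synopsis does not tie 'safe' to the count, so a rejected dose would not be safe in its sense. A sensible author would hardly call such a dose tolerated. This has force as a guide to intent. But the body of the protocol ties 'safe' to the count expressly, and a definition should not depend on its user's good sense.

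**Redaction.** Text is blacked out just before the sentence on the DSMC's power, the synopsis points to Section 8.2 for more on MTDs, and the Data Safety Monitoring Plan is not available. This lowers confidence. It does not remove the point: Section 8.2.3 is readable, and the synopsis prints the decision rules, the DSMC's power and the MTD definition in sequence without linking the last two.

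**Consequence.** Protocol 12.4.1 lists DLTs, not the MTD. Escalation stops after the ruling, and under Section 8.1 the DSMC chooses the doses for combination and duration cohorts. This stands in full and sets the severity.

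**Stronger readings that a reader might infer.**
- That the rejected dose must be named the MTD. The text permits either of two labels, so this is not certain.
- That patients would be treated at a rejected dose because of the label. Nothing in the documents assigns doses by the MTD.
- That the frequency of mislabelling can be read from DLT probabilities or from the share of dosing that falls outside Cycle 1. Neither measures how often the DSMC would rule against a dose, and the documents give no rate.
- That the MTDu is affected just as plainly. The DSMC's power is worded for dose and reaches duration only through the 'in kind' statements and the separate condition in Section 8.1.

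**Conclusion.** Wrong as written; minor. The definition gives an unsound result in one case: 0 or 1 DLT of 3 together with a DSMC ruling that the safe dose was exceeded. The rejected dose can then be reported as the MTD, or as safe with the MTD not reached. In the illustration the reported dose would be 6 instead of 3 mg/kg/d. That gap reflects the assumed dose ladder and is not an estimate of error, since the DSMC may add intermediate doses. No frequency is claimed.

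The effect is on the reported MTD and, by inference, the MTDu. Protocol Section 3.7 says PK data from the first four dose-finding sub-cohorts are in hand, which suggests that the early monotherapy steps have been passed. The rule still governs any later monotherapy step and the combination sub-cohorts. The conclusion assumes that no redacted text or unseen monitoring plan links the ruling to the MTD.

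**What to change.** In Section 8.2.3 and the synopsis:

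1. Define the MTD (MTDu) as the highest tested dose (duration) with DLT in fewer than 2 of 3 patients that lies below any level that met the two-of-three rule or that the DSMC ruled to exceed the safe dose (duration). Count DSMC-added intermediate doses as tested levels.
2. If no tested level was exceeded by either route, report 'MTD not reached' with the highest level tested. If the lowest tested level was exceeded, report the MTD as below it.
3. In Section 8.2.3, explain 'safe' as DLT in fewer than 2 of 3 patients and no DSMC ruling that the safe dose was exceeded.
4. Apply the same wording to the combination sub-cohorts, and state outright that the DSMC's power covers duration.

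The cost is a few clauses in two places. Cohort sizes, escalation rules and the outcome with two or more DLTs do not change, and the SAP follows by cross-reference. The downside is that the report may state a lower MTD or none.
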